Statistical Analysis Plan

for

Study Protocol

Intervention and Outcomes in Duarte Galactosemia

Principal Investigator [name]

IRB00081271

NCT02519504

Date 04/01/2019

Statistical Analysis Plan:

Our Statistical Analysis Plan, prepared in follow-up to multiple meetings of a "Data Analysis Subgroup" from our research team, is described below. In short, data were cleaned and relevant covariates were identified for each outcome. Next, our cohort of 350 volunteers (206 cases and 144 controls) was randomly subdivided into independent "discovery" (n=87) and "validation" (n=263) sets that were approximately balanced with regard to case/control composition and covariates. We then tested each of the 73 outcome variables collected for each subject for possible association with case/control status using data from the discovery cohort; though none met the bar for statistical significance after multiple test correction we simply ranked them by ascending p value. Finally, we tested the 10 outcomes with the smallest p values from this ranking for (a) possible association with case/control status in the validation set, and also (b) possible association among cases in the validation set with milk exposure in the first year of life. All statistical analyses were performed in R.

How the data were cleaned:

- 1. We imported study data from REDCap (PCORIDGStudy_R_2017-XX-XX_XXX.r) into R.
- We filtered subjects by participation status to include only those who completed both Part 1 and Part 2.
- 3. We filtered out subjects marked for exclusion from analysis (e.g. after testing we realized they should have been excluded).
- 4. We filtered out subjects whose DG status was unknown.
- 5. We created a new variable representing the highest education level of either parent/guardian.
- 6. We created a new ordinal variable for breast milk exposure.
 - Value (0, 1, 2, or 3) indicating the number of time intervals (birth to 1 month, 2 to 6 months, 7 to 12 months) during which the subject drank at least some breast milk.
- We created new variables for average ABERS latency values at each wave (i.e., average "aber_w1_lat" and "aber_st_w1_lat").
- 8. For each variable in the dataset we:

- a. Indicated category label: administrative variable, covariate, DG status variable, dairy exposure variable, or outcome variable.
- b. For covariates, we indicated whether the variable should be considered in Aim 1 (DG/non-DG analysis), Aim 2 (DG-only diet analysis), or both.
- c. For outcome variables, we indicated whether the variable should be considered in Aim 1 (DG/non-DG analysis), Aim 2 (DG-only diet analysis), or both.
- d. For outcome variables, we indicated the general domain of development under which it belonged.
- e. For each outcome variable, we indicated whether it had already been adjusted to account for any covariates and, if so, which ones (e.g., assessment score already normed for age and gender).
- f. Indicated data source (Part 1 survey, Part 2 testing).
- g. Indicated variable type (continuous, ordinal, categorical, binary).
- 9. For each variable, we plotted all data points and looked for outliers.
 - a. For continuous variables, we used a threshold of ± 3 SD from the mean.
 - b. If found, we confirmed with the testing team whether the outlier was genuine or a scoring/data entry error.
- 10. We cleaned and aggregated sparse categorical covariate levels where needed.
- 11. We compared "missingness" among outcome measures between DG cases and controls.
 - a. We tested whether the proportion of DG cases missing data on a given outcome differed significantly from the proportion of controls missing that outcome data.
 - b. We used a chi-square test if the number missing was large (i.e., expected counts >5) or
 Fisher's exact test if the number missing was small (i.e., expected counts <5).
 - c. If the proportion of missing data was significantly different between cases and controls, we could either: (1) exclude that outcome from analysis, or (2) impute missing data conditional on phenotype [see *Statistical Analysis with Missing Data* by Little and Rubin].
- 12. We calculated summary statistics for variables (from both Part 1 and Part 2 sources) across:(1) all subjects, (2) non-DG subjects only, (3) DG subjects only, (4) dairy-exposed DG subjects only, and (5) non-dairy exposed DG subjects only.

- We used mean, SD, median, and IQR for continuous variables.
- 13. For continuous variables, we checked to see if they followed a normal distribution using the Shapiro-Wilk Normality test. For non-normally distributed continuous variables, we tried transformation to achieve normality. If a log or square-root transformation failed to work, we used an inverse-normal transformation.

Covariate selection:

As we tested multiple outcome measures for association with DG status (Aim 1) and for association with diet among DG cases (Aim 2), for each of the outcomes considered, we identified the relevant covariates to adjust for. Using the steps described below, we determined the subset of covariates to be included in subsequent models for each outcome.

- 1. Using the information provided in step #8 above, we identified all variables that were to be initially considered as potential confounders for each outcome measure.
- 2. With these variables as predictors and the outcome measure of interest as the response variable, we used the R package *glmnet* to fit a generalized linear model with lasso regularization.
 - a. We used 10-fold cross-validation to determine the optimal lambda value.
 - b. We identified the subset of variables with non-zero coefficients and flagged these as covariates for subsequent models of the outcome.
 - c. Please note: This approach assumed observations were independent and did not take into account the shared familial structure of the dataset. As described below, in later analyses we used a mixed-model approach to account for relatedness among family members in the study.

Dividing our full cohort into independent discovery and validation sets:

Although data on 73 outcome variables were collected, our study was only adequately powered to test ~20 hypotheses due to the need to correct for multiple testing. As we sought both to test phenotypic differences between DG cases and controls, and also to test phenotypic differences associated with diet among cases, this substantially reduced the number of phenotypes we could consider without compromising the power of the data set. In order to find a balance between our desire to maintain adequate statistical power and our obligation to find differences in the data wherever they might exist, we first divided our sample into independent "discovery" and "validation" sets. We used the discovery set to identify the 10 outcome measures of greatest interest (smallest p value). We then used this subset of outcomes for a focused analysis of the validation set at an appropriate Bonferroniadjusted significance threshold.

- 1. We randomly selected ~25% of Part 2 study subjects for assignment to the discovery set.
 - To ensure independence of the discovery and validation sets, siblings were always assigned to the same set.
- 2. We assigned the remaining 75% of study subjects to the validation set.
- We repeated the random assignment process until an appropriate mix of DG cases/controls and dairy-exposed/non-exposed cases (close to original distribution in the full dataset) was achieved in each set.

Using the discovery data set to rank order outcome variables to test in the validation data set:

- In the discovery set, we fitted a mixed-effect regression model (linear, logistic, or ordinal) for each outcome variable that included DG status and all necessary covariates as predictors.
- 2. The mixed model approach allowed for clustering at the family level and therefore took into account relatedness among study subjects.
- 3. We ranked the models by resulting p-value for the DG status regression coefficient, and selected the 10 top-scoring outcomes between cases and controls.
- Even if no models showed significance at raw p<0.05 for association with DG, we choose the 10 outcomes with the smallest p-values.

Aim 1: Identify phenotypes associated with DG

1. We fit comparable models for the 10 outcomes showing the smallest p values in the

discovery set using data from the independent validation set.

2. Our goal was to identify any outcomes whose models showed significant association with DG status at the Bonferroni-adjusted p-value threshold ($\alpha = 0.05/20 = 0.0025$) in the validation set. There were none.

Aim 2: Identify phenotypes associated with diet among DG cases

While the random assignment process described above yielded a discovery set with a satisfactory number of both cases and controls to assume it was representative of the full study population, the number of dairy-exposed cases and non-exposed cases in the discovery set was not large enough to confidently consider it a representative sample. For this reason, we tested the same 10 outcome variables as above for association with diet among DG cases.

- 1. We filtered the discovery set generated as described above to include only DG cases.
- Using the discovery set, we fitted a mixed-effect regression model (linear, logistic, or ordinal) for each of the 10 selected outcome variables that included milk exposure and all necessary covariates as predictors.
- 3. Our goal was to identify any outcomes whose models showed significant association with diet among cases at a Bonferroni-adjusted p-value threshold ($\alpha = 0.05/20 = 0.0025$) in the discovery set. There were none.

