In Part 2 of the study we will gather information using a combination of parent-response surveys and direct child assessments, all non-invasive and all conducted or administered by trained professionals (details explained below). One parent-response survey will be administered online or by telephone prior to the actual direct testing appointment. The full schedule of assessments for any one child will take no more than 3½ to 4 hours, including breaks.

The only biological samples to be collected as part of this study are saliva samples (about 1 teaspoon full) to be collected from child participants during the direct assessment blocks using "spit kits." This process is simple and completely non-invasive – the volunteer literally spits into a small container. We will use this saliva to isolate DNA for *GALT* genotyping. By doing *GALT* genotyping on these volunteers we will confirm case versus control status and also identify the specific *GALT* mutations present in each case. This analysis will also reveal which sibling controls are carriers. The consent form signed on behalf of each child volunteer will provide a space where the parent or guardian can indicate whether or not they wish to be informed of their child's *GALT* genotype after participation.

Direct assessment blocks: We will conduct direct assessments of child outcome in each block using validated, standardized instruments administered by trained professionals. We will also collect child height,

weight, and head circumference, and biological parental heights, if available. The following developmental outcomes will be assessed: cognitive skills (especially memory, executive function, and auditory processing), communication processes (speech and language), physical development (including motor skills, coordination, and occurrence of tremors), and social-emotional development. The instruments we will use to quantify each of the outcome parameters are described below and listed in **Table 1**.

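### Aim 2 covariates are chosen by a lasso on the outcome alone, so listed confounders of infant diet can be dropped; the main risk is masking a real diet effect

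*SAP*

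**What the plan says.** The SAP describes one selection procedure for both aims, by which "we determined the subset of covariates to be included in subsequent models for each outcome". Step 2 of Covariate selection takes the candidate variables "With these variables as predictors and the outcome measure of interest as the response variable" and uses glmnet to "fit a generalized linear model with lasso regularization". On the penalty it says: "We used 10-fold cross-validation to determine the optimal lambda value". On retention it says: "We identified the subset of variables with non-zero coefficients and flagged these as covariates for subsequent models of the outcome". The Aim 2 model then contains milk exposure plus the covariates so flagged.

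Two steps under How the data were cleaned bear on this. Step 8a sorts variables into the classes "administrative variable, covariate, DG status variable, dairy exposure variable, or outcome variable". Dairy exposure is thus a separate class from covariate and appears not to enter the lasso. Step 8b reads: "For covariates, we indicated whether the variable should be considered in Aim 1 (DG/non-DG analysis), Aim 2 (DG-only diet analysis), or both". That step governs entry to the candidate pool, not retention.

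The protocol's opening section says that providers differ on whether these infants should drink soy formula, so diet followed advice and family choice. Its Table of Measures names prenatal or postnatal tobacco and alcohol exposure, family socioeconomic status and caregiver stress as potential covariates or confounders. Under Procedures it adds that, by genotyping saliva, "we will confirm case versus control status and also identify the specific" GALT mutations of each case. SAP cleaning step 5 derives the highest parental education. No step in the SAP guarantees any of these a place in the diet models.

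**The concern.** A confounder needs a link to exposure and a link to outcome. A lasso tuned to predict the outcome judges only the second. A variable strongly tied to diet and modestly tied to the outcome is therefore easily dropped, although omitting it biases the diet coefficient.

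Aim 2 asks whether early milk exposure matters for these children. Residual confounding could create an association or hide one, and a strict significance threshold does not correct bias. The SAP reports that no outcome reached the threshold for diet, so the second possibility bears on how the result should be read.

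**Working it through.** **1. Plan's own figures.** Ten outcomes in two aims give 20 tests, and 0.05/20 = 0.0025, as stated. The counts agree: 206 + 144 = 350 and 87 + 263 = 350. Pro rata, the validation set holds 206 × 263/350 = 154.8, about 155 cases, and the discovery set 206 × 87/350 = 51.2, about 51. The SAP's opening summary places the Aim 2 test in the validation set, while its Aim 2 section places it in the discovery set.

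**2. Assumptions (none is in the documents).** Continuous outcome with residual SD 1; half the cases exposed; independent normal covariates; 15 candidates. Of these, K are confounders with slope b (SD per SD) on the outcome and correlation r with the latent tendency to be exposed. One further candidate has slope 0.3. Selection uses 206 cases and the test 155; no family clustering; 1,000 runs per setting.

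**3. Confounding with no adjustment.** With a 50% split, each confounder differs between diet groups by r × 2 × 0.798 = 1.596r, so the bias is K × b × 1.596r.
- K=1, b=0.10, r=0.5: 0.080 (simulated 0.077)
- K=3, b=0.10, r=0.4: 0.192 (simulated 0.188)
- K=3, b=0.15, r=0.4: 0.287 (simulated 0.297)

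**4. No true diet effect, SAP rule.**

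| Setting | Penalty | Each confounder dropped | Bias (SD) | Rejected at 0.05 | Rejected at 0.0025 |
|---|---|---|---|---|---|
| K=1, b=0.10 | minimum error | 53% | 0.02 | 4.7% | 0.2% |
| K=1, b=0.10 | one-SE | 97% | 0.07 | 7.2% | 0.4% |
| K=3, b=0.10 | minimum error | 45% | 0.04 | 4.8% | 0.4% |
| K=3, b=0.10 | one-SE | 95% | 0.17 | 15.6% | 1.9% |
| K=3, b=0.15 | minimum error | 18% | 0.04 | 5.0% | 0.4% |
| K=3, b=0.15 | one-SE | 80% | 0.21 | 25.9% | 4.3% |

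The one-SE rule leaves 0.166/0.188 = 88% of the confounding in the second setting and 0.214/0.297 = 72% in the third. For K=3, b=0.10, testing on 51 cases gives a bias of 0.05 (minimum error) or 0.17 (one-SE); selecting on all 350 subjects gives 0.02 or 0.16. Adjusting for all candidates, or for the union of an outcome lasso and an exposure lasso, gives a bias of at most 0.02 SD, with rejection of 4.3 to 5.7% at 0.05 and 0 to 0.3% at 0.0025.

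**5. Dependence on the candidate pool (minimum error).** With three confounders at 0.10 (200 runs per setting), bias was 0.05 SD with 15 candidates and 0.08 SD with 30; rejection was 4 to 7% at 0.05 and 0 to 0.5% at 0.0025. With 30 candidates, no strong predictor, three or four confounders and log-odds of 0.8 per SD on diet (400 runs), the lasso returned an empty model in 35 to 36% of runs. Bias was 0.09 to 0.11 SD, with rejection of 8.5 to 10% at 0.05 and 0.5 to 0.75% at 0.0025. With 25 to 40 candidates and three to five confounders, bias reached 0.12 SD. With five strong predictors present it fell to 0.02 SD.

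**6. Masking.** Suppose a true effect d = -0.50 SD and confounding of opposite sign. With exposure left out of the lasso, a confounder's marginal slope is b + d × 0.399r.
- K=1, b=0.20, r=0.5: 0.20 - 0.50 × 0.399 × 0.5 = 0.10
- K=3, b=0.15, r=0.4: 0.15 - 0.50 × 0.399 × 0.4 = 0.07

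The lasso sees a weakened signal. In the K=3, b=0.15 setting, drops under minimum error rise from 18% to 64%.

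| Setting | Adjustment | Dropped | Mean estimate | Power at 0.0025 |
|---|---|---|---|---|
| K=1, b=0.20 | all candidates | – | -0.50 | 36% |
| K=1, b=0.20 | minimum error | 53% | -0.42 | 27% |
| K=1, b=0.20 | one-SE | 97% | -0.34 | 14% |
| K=3, b=0.15 | all candidates | – | -0.49 | 26% |
| K=3, b=0.15 | minimum error | 64% | -0.34 | 12% |
| K=3, b=0.15 | one-SE | 98% | -0.22 | 4% |

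Union selection gave -0.49 in both settings, with power of 37% and 28%.

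**The case against.** The strongest reply is about size. The documents give no number of candidates and no covariate associations, so every figure above rests on assumed inputs. The diet links are strong: r = 0.4 implies a difference of 1.596 × 0.4 = 0.64 SD per confounder between diet groups. In the 25-to-40-candidate settings, log-odds of 0.8 per SD imply that the confounders alone predict diet with an AUC of about 0.80 to 0.84. Real covariates such as education and socioeconomic status would probably correlate, so a retained one would partly adjust for a dropped one. The penalty wording most naturally means the minimum-error value. The team also screened candidates by aim (step 8b), treated the pool as possible confounders (Covariate selection, step 1) and recorded which scores were already normed (step 8e). All of this stands as a limit on size. None of it secures retention.

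A reader might infer serious false-positive inflation. Rates of 9 to 16% at 0.05 do arise with 25 to 40 candidates, no strong predictor and all 206 cases tested (0.6 to 1.7% at 0.0025). No Aim 2 test uses 206 cases, the plan tests at 0.0025, and no positive finding was reported. The 14 to 31% seen at 0.05 with a one-SE penalty in such settings rests on a rule the SAP does not state.

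Masking also needs an assumption: confounding opposite in sign to a real effect. Even full adjustment has only 26 to 36% power at 0.0025 in those settings. So confounder loss would be one of several reasons for a null result.

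**Conclusion.** The point holds as a weakness of method. Selection ignores milk exposure and forces nothing in, so confounders that the protocol lists can be lost from the diet models. The documents do not fix the size. Under the stated assumptions, minimum-error selection leaves about 0.02 to 0.12 SD of bias. With 155 cases tested, it gives at most about 0.75% false positives at 0.0025, and 0.2 to 0.4% with 15 candidates. The one-SE rule, if used, leaves most of the confounding.

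Masking is the main concern after a null result, and the minimum-error rule does not prevent it: power fell from about 36% to 27%, or from 26% to 12%. A reader might go further and infer that the reported null is wrong or that bias occurred. The documents do not support that, because they give neither the selected covariates nor their links to diet. What follows is that the null on diet is less secure than the plan implies.

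**What to change.** - In every Aim 2 model, keep the protocol's listed potential confounders: family socioeconomic status including parental education, and prenatal and postnatal tobacco and alcohol exposure. Use caregiver stress only in a sensitivity model, since it is measured after the diet exposure.
- Alternatively, add a second lasso with milk exposure as the response and adjust for the union of the two selected sets. In either case, use the outcome lasso only to add precision covariates.
- Add age and sex only for outcomes not already normed for them. Use GALT genotype where cell sizes allow.
- Do not force in state. Fourteen listed states mean 13 indicators for about 51 or 155 cases. If state mainly reflects local diet advice, it costs precision and can amplify residual confounding.
- State the penalty rule, whether selection used cases only, and which set the Aim 2 test uses; the two SAP statements on the set must be reconciled.
- As results are already reported, the minimum is a sensitivity analysis that retains the listed confounders.

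The covariates are already collected, so this needs one SAP paragraph and a few lines of R. The price is precision: in one simulated setting the standard error rose from about 0.17 to 0.19 SD (0.19/0.17 = 1.12), and it rose by about 10 to 20% where confounder-diet links were strong.

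### The statement that the study was adequately powered for about 20 hypotheses has no stated basis and is not shown for the subsets in which the 20 tests are run; for Aim 2 in discovery-set cases it is not credible.

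*SAP*

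**What the plan says.** The SAP section on dividing the cohort into discovery and validation sets states that "our study was only adequately powered to test ~20 hypotheses due to the need to correct for multiple testing". It offers this as the reason for splitting the sample and carrying forward only ten outcomes. The opening summary gives the base as "our cohort of 350 volunteers (206 cases and 144 controls", "randomly subdivided into independent 'discovery' (n=87) and 'validation' (n=263) sets that were approximately balanced with regard to case/control composition and covariates".

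Ten outcomes in each of two aims make 20 tests. Aim 1 looks for "significant association with DG status at the Bonferroni-adjusted p-value threshold ($\alpha = 0.05/20 = 0.0025$) in the validation set". For Aim 2 the SAP gives two different data sets. The opening summary describes a test of "possible association among cases in the validation set with milk exposure in the first year of life". The Aim 2 section says "Using the discovery set, we fitted a mixed-effect regression model (linear, logistic, or ordinal) for each of the 10 selected outcome variables", and judges the results by "significant association with diet among cases at a Bonferroni-adjusted p-value threshold ($\alpha = 0.05/20 = 0.0025$) in the discovery set". Both aims report no significant outcome.

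The protocol plans at least 144 cases and at least 144 controls for Part 2, with no power calculation.

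**The concern.** The power statement concerns the study and comes before the account of the split, so a reader will take it to describe the full cohort. All 20 tests are then run in smaller sets. Aim 2 loses twice: it drops the controls and it uses only part of the cases. Adequacy in 350 children, if it was ever established, does not carry over to these sets.

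What is at stake is how the null results are read. If the 20 tests are understood to be adequately powered, finding nothing looks like evidence that there is little to find. This matters most for diet in infancy, which is the protocol's second specific aim and has the fewest children behind it.

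**Working it through.** **The plan's own figure.** 0.05/20 = 0.0025 reproduces. The figure of about 20 hypotheses cannot be reproduced, because no effect size, SD, power target or sample size is given for it.

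**Inputs from the SAP.** Full cohort 350 (206 cases, 144 controls); discovery 87; validation 263.

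**Assumptions.** Two-sided tests; continuous outcomes in SD units; normal approximation; independent children (no family clustering, covariates or missing data). Case counts by set are not stated, so a proportional split is taken: 206 × 263/350 ≈ 155 and 144 × 263/350 ≈ 108 in validation; 206 × 87/350 ≈ 51 cases in discovery. The exposure split among cases is not stated; 1:1, 2:1 and 80/20 are shown.

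**Step 1: what the split does to power, without choosing an effect size.** With the group ratio unchanged, the expected test statistic scales with √(n/N). The critical value at 0.0025 is z = 3.023. An effect with 80% power before the split has expected statistic 3.023 + 0.842 = 3.865; for 90% it is 3.023 + 1.282 = 4.305.

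- Validation, √(263/350) = 0.867. From 80%: 3.865 × 0.867 = 3.350, and Φ(3.350 − 3.023) = 63%. From 90%: 76%.
- Discovery, √(87/350) = 0.499. From 80%: 3.865 × 0.499 = 1.927, and Φ(1.927 − 3.023) = 14%. From 90%: 19%.
- Among cases only, 155 of 206 and 51 of 206 give the same figures to the nearest percent: 63% and 14% from 80%, 76% and 19% from 90%.

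To keep 80% in the validation set, power before the split would have to be Φ(3.865/0.867 − 3.023) ≈ 92%.

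**Step 2: difference detectable with 80% power at 0.0025.** Formula: 3.865 × √(1/n₁ + 1/n₂).

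| Test | Groups | Detectable difference (SD) |
|---|---|---|
| Aim 1, full cohort (not used) | 206 v 144 | 3.865 × 0.1086 = 0.42 |
| Aim 1, validation | 155 v 108 | 3.865 × 0.1253 = 0.48 |
| Aim 2, validation cases, 1:1 | 78 v 77 | 3.865 × 0.1606 = 0.62 |
| Aim 2, validation cases, 2:1 | 103 v 52 | 3.865 × 0.1701 = 0.66 |
| Aim 2, validation cases, 80/20 | 124 v 31 | 3.865 × 0.2008 = 0.78 |
| Aim 2, discovery cases, 1:1 | 26 v 25 | 3.865 × 0.2801 = 1.08 |
| Aim 2, discovery cases, 2:1 | 34 v 17 | 3.865 × 0.2970 = 1.15 |

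**Step 3: power at a fixed difference.** Formula: Φ(d/√(1/n₁ + 1/n₂) − 3.023). At 0.5 SD, Aim 1 in validation has 83%. Aim 2 has 54% (1:1) to 30% (80/20) in validation cases, and 11% (1:1) in discovery cases. At 0.8 SD, Aim 2 has 98% (1:1) to 83% (80/20) in validation cases but only 43% (1:1) in discovery cases.

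**Step 4: a base more favourable to the plan.** Suppose the figure of 20 was worked out for the 155 validation cases themselves. With √(51/155) = 0.574, an effect with 80% power there has Φ(3.865 × 0.574 − 3.023) = 21% in 51 discovery cases; from 90% it is 29%.

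**The case against.** The strongest reply is that adequacy cannot be refuted when no effect size or power target is stated. This stands for Aim 1. A 0.5 SD difference has 83% power in the validation set, and the figure of 20 may already have allowed for the split. The base may also be the protocol's planned 144 v 144: an effect with 90% power there is 4.305 × 0.1179 = 0.51 SD, which has about 85% power in 155 v 108. A reader might infer that the claim fails in every subset; the documents do not support that.

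A reader might also take the 0.42 SD case-control difference from the full cohort and apply it to the diet comparison, which would make Aim 2 look weaker still. Nothing in the documents says that the two effects should be equal. The like-for-like loss within cases, in step 1, is the fair comparison.

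Third, the discovery-set wording under Aim 2 may be a slip. The opening summary says validation, and the Aim 2 section itself concedes that the diet groups in the discovery set were too few to be representative. That is possible, but the section names the discovery set in the filtering, the model fitting and the reported result, so the text cannot be set aside without a correction.

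Finally, the SAP states a ceiling on the number of tests and does not say that the null results exclude effects. That is fair. But a ceiling on what is adequately powered still implies that tests within it are adequate.

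**Conclusion.** The concern holds as a matter of degree. The power statement has no stated basis, and on its natural reading it describes a cohort that no confirmatory test uses.

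- **Aim 1:** not shown. Power reaches 80% only from about 0.48 SD; inadequacy is not proved.
- **Aim 2 in validation cases:** doubtful. It needs about 0.62 SD (1:1), 0.66 SD (2:1) or 0.78 SD (80/20).
- **Aim 2 in discovery cases, as the Aim 2 section is written:** not credible. It needs about 1.08 SD or more. A ceiling of only about 20 tests suggests an effect near the detection limit, and sizing it on the full cohort, all cases or the validation cases at 80% or 90% power leaves at most 29% there.

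These figures rest on the assumptions listed with the inputs above. SD units do not apply directly to the binary and ordinal outcomes. The figures also take each outcome as already selected, so they ignore the chance that a truly associated outcome misses the discovery ranking.

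**What to change.** 1. Reconcile the opening summary and the Aim 2 section on which set the Aim 2 tests used. At a 1:1 exposure split the answer moves the detectable difference from about 0.62 to 1.08 SD.
2. Replace the sentence about 20 hypotheses with the detectable difference for each aim in the set actually used, computed from the real case, control and exposure counts, and on a suitable scale for binary and ordinal outcomes. Say whether family clustering and covariates are allowed for; the approximations here ignore both.
3. Do not describe the Aim 2 null results as coming from adequately powered tests. Report all 20 results with confidence intervals.

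If the summary is right about the Aim 2 set, this changes only SAP wording and reporting. The cost is that the stated power becomes less favourable, above all for Aim 2.
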